8.3.1. Time Period and Frequency for Collecting AE and SAE Information

[figure not shown]
All SAEs will be collected from the signing of the ICF until the follow-up visit at the time points specified in the SoA ([Table 1](#)).

All AEs will be collected from the signing of the ICF until the follow-up visit at the time points specified in the SoA ([Table 1](#)).

All SAEs will be recorded and reported to the Sponsor or designee immediately and under no circumstance should this exceed 24 hours, as indicated in [Appendix C](#). The Investigator will submit any updated SAE data to the Sponsor within 24 hours of it being available.

Investigators are not obligated to actively seek information on AEs or SAEs after conclusion of the study participation. However, if the Investigator learns of any SAE, including a death, at any time after a participant has been discharged from the study, and he/she considers the event to be reasonably related to the study intervention or study participation, the Investigator must promptly notify the Sponsor within 24 hours of awareness.

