
• Any abnormal laboratory test results (hematology, clinical chemistry, or urinalysis) or other safety assessments (e.g., ECG, radiological scans, vital signs measurements), including those that worsen from baseline, considered clinically significant and not related to underlying disease progression, in the medical and scientific judgment of the Investigator.• Exacerbation of a chronic or intermittent pre-existing condition including either an increase in frequency and/or intensity of the condition.• New conditions detected or diagnosed after study intervention administration even though it may have been present before the start of the study.• Signs, symptoms, or the clinical sequelae of a suspected intervention- intervention interaction.• Signs, symptoms, or the clinical sequelae of a suspected overdose of either study intervention or a concomitant medication. Overdose per se will not be reported as an AE/SAE unless it is an intentional overdose taken with possible suicidal/self-harming intent. Such overdoses should be reported regardless of sequelae.

Events NOT Meeting the AE Definition

• Any clinically significant abnormal laboratory findings or other abnormal safety assessments that are associated with the underlying disease, unless judged by the Investigator to be more severe than expected for the participant's condition.• The disease/disorder being studied or expected progression, signs, or symptoms of the disease/disorder being studied, unless more severe than expected for the participant's condition.• Medical or surgical procedure (e.g., endoscopy, appendectomy): the condition that leads to the procedure is the AE.

- Situations in which an untoward medical occurrence did not occur (social and/or convenience admission to a hospital).
- Anticipated day-to-day fluctuations of pre-existing disease(s) or condition(s) present or detected at the start of the study that do not worsen.

Laboratory Test Result Abnormalities

The criteria for determining whether an abnormal objective test finding should be reported as an AE are as follows:

- Test result is associated with accompanying symptoms;
and/or
- Test result requires additional diagnostic testing or medical/surgical intervention;
and/or

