An event is defined as ‘serious’ when it meets at least 1 of the predefined outcomes as described in the definition of an SAE, **NOT** when it is rated as severe.

Assessment of Causality

- The Investigator is obligated to assess the relationship between study intervention and each occurrence of each AE/SAE.
- A “reasonable possibility” of a relationship conveys that there are facts, evidence, and/or arguments to suggest a causal relationship, rather than a relationship cannot be ruled out.
- The Investigator will use clinical judgment to determine the relationship.
- Alternative causes, such as underlying disease(s), concomitant therapy, and other risk factors, as well as the temporal relationship of the event to study intervention administration will be considered and investigated.
- The Investigator will also consult the IB and/or Product Information, for marketed products, in his/her assessment.
- For each AE/SAE, the Investigator **must** document in the medical notes that he/she has reviewed the AE/SAE and has provided an assessment of causality.
- There may be situations in which an SAE has occurred and the Investigator has minimal information to include in the initial report to Medpace Clinical Safety. However, it is very important that the Investigator always assess causality for every event before the initial transmission of the SAE data to Medpace Clinical Safety.
- The Investigator may change his/her opinion of causality in light of follow-up information and send an SAE follow-up report with the updated causality assessment.
- The causality assessment is one of the criteria used when determining regulatory reporting requirements.

Follow-up of AEs and SAEs

- The Investigator is obligated to perform or arrange for the conduct of supplemental measurements and/or evaluations as medically indicated or as requested by the Sponsor/Medical Monitor to elucidate the nature and/or causality of the AE or SAE as fully as possible. This may include additional laboratory tests or investigations, histopathological examinations, or consultation with other health care professionals.
- New or updated information will be recorded in the originally submitted documents.
- The Investigator will submit any updated SAE data to Medpace Clinical Safety within 24 hours of receipt of the information.

C.4 Reporting of SAEs**SAE Reporting to Medpace Clinical Safety via an Electronic Data Collection Tool**

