#### **Missing/Partial Dates:**

- In cases of incomplete dates for AEs and concomitant medications, the missing component(s) will be assumed as the most conservative value possible. No imputation of start/end dates or times will be performed.
  - If a medication date is missing or partially missing and it cannot be determined whether it was taken prior or concomitantly, it will be considered a concomitant medication.
  - AEs with incomplete start date and times will be attributed to the treatment according to the following algorithm:
    1. Only the day is reported: The event will be considered treatment emergent unless the end date is present and indicates that the event ended prior to the first dose date.
    2. Only the start year or the day and start year is reported: If the year is after or the same as the year of the first dose date, then the event will be considered treatment emergent unless the end date is present and indicates that the event ended prior to the first dose date.
    3. Only the start month and year are reported: If the month/year is after or the same as the month/year of the first dose date, then the event will be considered treatment-emergent unless the end date is present and indicates that the event ended prior to the first dose date.
    4. Only the time is missing: If the time is missing, but the start date otherwise matches the date of first dose, then the event will be considered treatment-

emergent unless the end date and time are present and indicate that the event ended prior to the first dose date and time.

For treatment-emergent adverse events (TEAEs), time since first dose will be calculated as the difference between the event start date and the first date of dosing plus one and expressed in days. Time since first dose will not be calculated if the start date is partial.

Duration will be calculated for AEs that resolve as the difference between the resolution date and onset date and will be expressed in days, hours and minutes. If either time is missing, duration will be calculated as the difference between the resolution date and onset date plus one and expressed in days. Time since dose and duration will only be calculated when both dates are complete.

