### 3.1.8 *Treatment-Emergent Adverse Event (TEAE)*

A TEAE is defined as an AE that emerges after the first dose of EDG-5506, having been absent at pretreatment (BL) or:

- Reemerges during treatment, having been present at pretreatment (BL) but stopped before treatment, or
- Worsens in severity during treatment relative to the pretreatment state when the AE is continuous.

Treatment-emergence will be determined by comparing the start date and time of the AE with the actual date and time of first dose of EDG-5506. If the onset date of an AE is missing and the AE resolution date is either after the initial EDG-5506 dose date or is missing, then the AE will be considered treatment emergent. If the onset time of an AE is missing and the start date of the AE is on or before the EDG-5506 dose date, then the AE will be considered treatment emergent.

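### SAP 3.1.8 sets the TEAE flag from the AE start date and time, so it can miss a pre-dose AE that worsens on drug and can flag one that never worsened

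*SAP*

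**What the plan says.** SAP 3.1.8 first defines a TEAE. It is an AE that appears after first dose, one that was present before treatment, stopped and came back during treatment, or one that meets the third limb: "Worsens in severity during treatment relative to the pretreatment state when the AE is continuous".

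The next paragraph says how the flag is set: "Treatment-emergence will be determined by comparing the start date and time of the AE with the actual date and time of first dose". Two defaults follow, and each makes the AE treatment-emergent when its condition is met:

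- Missing onset date: "If the onset date of an AE is missing and the AE resolution date is either after the initial EDG-5506 dose date or is missing".
- Missing onset time: "If the onset time of an AE is missing and the start date of the AE is on or before the EDG-5506 dose date".

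SAP 3.1.7 adds an algorithm for partial start dates. For a known month and year (item 3) the test is "If the month/year is after or the same as the month/year of the first dose date", with an exception for events whose end date shows that they finished before first dose. Item 4 covers a missing time, but only where the start date is the first-dose date, and it has the same kind of end-date exception.

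On recording, Protocol 8.3.1 states: "All AEs will be collected from the signing of the ICF until the follow-up visit". Protocol Appendix C.1 lists this among events that are AEs: "Exacerbation of a chronic or intermittent pre-existing condition including either an increase in frequency and/or intensity of the condition". Appendix C.3 says of follow-up: "New or updated information will be recorded in the originally submitted documents".

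**The concern.** A continuous AE that was present before treatment has, by construction, a start date before first dose. A rule that looks only at the start date and time cannot detect that it later worsened. The definition and the rule that is meant to implement it therefore give different answers for the case the third limb was written for. Neither document supplies a separate worsening rule, and neither says that a worsening is entered as a new AE record with its own start date.

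The missing-time default has the opposite fault. It admits AEs that began before the dose date and are unchanged or already over, so an AE that was severe before treatment could enter the count by maximum severity.

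The flag feeds the AE overview in SAP 3.5.1.2 (TEAEs overall and by maximum severity, drug-related TEAEs, TEAEs leading to discontinuation), the matching tables by SOC and PT, and the TEAE incidences promised in Protocol 9.4.2. In a study this small, one participant is visible in every such percentage.

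**Working it through.** The plan gives no figure to reproduce. The check is to apply the definition, and then the deciding rule with its defaults (all in SAP 3.1.8), to the same AE patterns.

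| Pattern | Definition | Deciding rule and defaults |
|---|---|---|
| A. Pre-dose start, date and time known, continuous, worsens, one record | TEAE | Not TEAE |
| B. As A, start time missing | TEAE | TEAE |
| C. As A, start date missing, ongoing | TEAE | TEAE |
| D. Worsening entered as a new record dated after first dose | TEAE | TEAE |
| E. Pre-dose start, time known, no worsening | Not TEAE | Not TEAE |
| F. Pre-dose start, time missing, no worsening | Not TEAE | TEAE |
| G. Pre-dose start, time missing, resolved before first dose | Not TEAE | TEAE |
| H. Starts and ends on the first-dose date before the dose; onset time missing, end time known | Not TEAE | TEAE |

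The two disagree in A (an event missed) and in F, G and H (events added). H is a direct contradiction between sections: 3.1.7 item 4 excludes the event through its end-date exception, and 3.1.8 includes it. For F and G, item 4 is silent because the start date is not the first-dose date, so only the 3.1.8 sentence applies.

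**A sign that the third limb was not carried through.** SAP 3.1.7 computes time since first dose for a TEAE as start date minus first-dose date, plus one. For an AE that starts the day before dosing this is −1 + 1 = 0, although SAP 3.1.2 says there is no Day 0. Two days before dosing it is −2 + 1 = −1. The formula does not fit a worsening TEAE that keeps its original start date.

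**Exposure to the problem.** In the Schedule of Activities, consent is at Screening, on Day −1 with a window of −2 days, so Day −3 to Day −1. With no Day 0, that is 1 to 3 days before first dose.

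**Size of one misclassification.** The target is about 8 evaluable participants (SAP 2.5): 1/8 = 12.5 percentage points. Protocol 2.3.1 reports 12 adults with BMD dosed by May 2022; with that as an illustrative denominator, 1/12 = 8.3 points. The eventual size of the safety population is not stated.

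**The case against.** The best defence is that the gap is narrow and may already be closed in practice.

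- The defaults for a missing onset time, a missing onset date and many partial dates flag the AE anyway (B and C).
- Appendix C.1 treats exacerbation of a pre-existing condition as an AE in its own right. Its natural start date is the exacerbation, which passes the date rule (D). The case report completion guidelines and the programming specifications are separate documents and may say so.
- The pre-dose window is 1 to 3 days. Appendix C.1 also excludes expected symptoms of the disease unless they are more severe than expected.
- The primary endpoint is worded in terms of AEs and SAEs. SAP 3.5.1.2 tabulates all AEs at the highest severity reported, Appendix A has all-AE tables (14.3.2.1, 14.3.2.2), and Listing 16.2.7.1.1 shows every AE.

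Most of this stands as a limit on size. It does not remove the contradiction. The SAP states the deciding rule outright, and for pattern A that rule returns the wrong answer. Appendix C.1 does not say which start date an exacerbation receives, and the Appendix C.3 sentence on updates is compatible with one record that keeps its original start date. The defaults that rescue B and C are also not a worsening rule: the missing-time sentence flags B and F alike, without regard to whether severity changed.

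**Conclusion.** The rule is wrong as written, with a small expected effect. The deciding rule in SAP 3.1.8 does not implement the worsening limb of its own definition, and its missing-time sentence over-includes and conflicts with 3.1.7 item 4.

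Three stronger readings are tempting, and the documents do not support them:

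- A reader might infer that a worsening AE can never be a TEAE. Patterns B, C and D show otherwise; the miss is confined to a single record with a complete pre-dose start date and time.
- A reader might infer a one-way bias toward fewer TEAEs. F, G and H push the count up.
- A reader might infer that the event disappears from the primary safety results. Only TEAE-labelled counts change; the all-AE tables and listings still show it.

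The documents give no count of AEs ongoing at first dose and no rate of worsening, so the expected number of misclassified participants cannot be computed. The 12.5-point figure is the effect of one participant among 8, not a forecast. How often pattern A arises depends on the CRF recording convention and on whether onset times are captured, and neither is stated. No hypothesis test is planned, so no inference is affected. The case for acting rests on the flag's role in the safety overview and the low cost of correcting it.

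**What to change.** Before database lock, amend SAP 3.1.8 as follows:

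1. Limit the comparison of start date and time with first dose to new-onset and re-emergent events.
2. Add a worsening rule: an AE with onset before first dose whose severity increases on or after first dose is a TEAE, with its TEAE onset at the date of the increase and graded at the worsened severity. If dates of severity change are not collected, compare maximum on-treatment severity with pre-dose severity instead.
3. Replace the missing-time sentence so that it applies only when the start date equals the first-dose date, with the end-date exception of 3.1.7 item 4.

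With these changes all eight patterns agree with the definition: A is flagged, F, G and H are not, and B to E keep their present result. Where the date of increase is available, time since first dose for a worsening TEAE should run from that date. A line in the CRF completion guidelines should say how a worsening is recorded, for example as a new record dated at the increase.

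The cost is SAP wording, one or two programming conditions and a CRF note. TEAE counts may shift slightly in either direction.

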6.1.1. Administration of EDG-5506

EDG-5506 will be provided as a 2.5 mg or 10 mg tablet. It should be taken at night prior to bedtime, with or without food. Time of dose will be recorded in the participant diary through the Month 12 visit, at that point only time of dose the night prior to PK collections are required.

Refer to the Pharmacy Manual for information about missed doses.

Treatment-experienced participants will take the first dose of EDG-5506 at the site, in the morning on Day 1 to support the PK collection. Participants will continue dosing at home, starting in the evening on Day 2.

Treatment-naïve participants will take the first dose of EDG-5506 at the site in the morning on Day 1 and return to the site on Day 2 to complete the last PK timepoint before taking the second dose. Participants will remain at the site on Day 2 to be observed for a minimum of 2 hours post dose. Participants will continue dosing at home, starting in the evening on Day 3 after travel home from the site has been completed.

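### SAP 3.1.8 flags an AE that started before first dose as treatment-emergent whenever its onset time is missing, against the section's own definition

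*SAP*

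**What the plan says.** SAP 3.1.8 opens with the definition: "A TEAE is defined as an AE that emerges after the first dose of EDG-5506", having been absent at baseline. Two further routes are allowed. The AE may have stopped before treatment and come back during it. Or, if it was continuous, it qualifies when it "Worsens in severity during treatment relative to the pretreatment state when the AE is continuous". Emergence is decided by "comparing the start date and time of the AE with the actual date and time of first dose of EDG-5506".

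The section closes with two missing-data rules. If the onset date is missing, the AE is a TEAE when its resolution date is after the initial dose or is also missing. If only the onset time is missing, the AE is flagged when the "start date of the AE is on or before the EDG-5506 dose date, then the AE will be considered treatment emergent". This second rule has no condition on worsening, re-emergence or end date.

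Item 4 of the partial-date algorithm in SAP 3.1.7 also deals with a missing time, on narrower terms. It applies as follows: "If the time is missing, but the start date otherwise matches the date of first dose". Such an event counts as treatment "emergent unless the end date and time are present and indicate that the event ended prior to the first dose date and time".

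Protocol 8.3.1 sets the collection period: "All AEs will be collected from the signing of the ICF until the follow-up visit". Pre-dose AEs can therefore be in the database.

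**The concern.** When the start date is known and falls before the first dose, the comparison that 3.1.8 asks for is already settled, and a missing clock time cannot change it. Yet the last sentence uses the missing time as grounds to flag the event. Two AEs that both began the day before dosing and never worsened would be classified differently only because one has a time recorded. An AE that resolved before any drug was given could also be reported as treatment-emergent.

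Safety is the primary objective, and the flag feeds the TEAE incidence rates in Protocol 9.4.2. In SAP 3.5.1.2 it feeds the TEAE rows of the overview and the tabulations of TEAEs and treatment-emergent SAEs by system organ class and preferred term. In a study of about 8 evaluable participants, one wrong flag can visibly move a row. Two programmers following 3.1.7 and 3.1.8 respectively would also derive different flags from the same record.

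**Working it through.** The plan gives no figure to reproduce: the sample size is empirical and no hypothesis is tested. The check is to apply each rule to the same records.

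**1. Classification.** Take AEs with a known start date, no onset time, and no worsening or re-emergence. Let the start day run from Day -3 to Day 2 (SAP 3.1.2: first dose is Day 1 and there is no Day 0). Let the end day be any day from the start day to Day 2, or absent.

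| Start day | End-day patterns | 3.1.8 definition and date comparison | 3.1.8 last sentence | 3.1.7 item 4 |
|---|---|---|---|---|
| -3 | 6 | not TEAE | TEAE | does not apply; not TEAE by date |
| -2 | 5 | not TEAE | TEAE | does not apply; not TEAE by date |
| -1 | 4 | not TEAE | TEAE | does not apply; not TEAE by date |
| 1 | 3 | date alone cannot decide | TEAE | TEAE by default |
| 2 | 2 | TEAE | does not apply; TEAE by date | does not apply; TEAE by date |

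- Conflicts: 6 + 5 + 4 = 15 of the 15 patterns with a pre-dose start. Of these, 3 + 2 + 1 = 6 also ended before Day 1.
- No conflict: the 3 + 2 = 5 patterns starting on Day 1 or Day 2.
- If the last sentence is limited to the first-dose date, all 15 become not TEAE and the other 5 are unchanged.

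These are logical patterns, not expected frequencies.

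**2. The Day 1 exception.** The table does not model end times. A Day 1 AE with no onset time, but with an end date and time before the dose, is exempt under 3.1.7 item 4 and flagged under 3.1.8. This should be rare, because the first dose is early in the day: "Treatment-experienced participants will take the first dose of EDG-5506 at the site, in the morning on Day 1". Treatment-naïve participants also take it that morning.

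**3. Consistency with neighbouring rules.**
- Under 3.1.8, an AE with no onset date that resolved before the initial dose is not flagged. An AE with a known pre-dose date and only the time missing is flagged even if it resolved before dosing. The better-documented event gets the looser rule.
- SAP 3.1.7 computes time since first dose for TEAEs as start date minus first-dose date plus one. For an AE starting the day before dosing this is -1 + 1 = 0, although 3.1.2 has no Day 0. The formula fits TEAEs that start on or after the first-dose date.

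**4. Size of the pre-dose period.** The Schedule of Activities puts Screening at Day -1 with a window of -2 days. That gives Days -3 to -1, about 3 days, if consent is signed at that visit.

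**5. Effect on a table row.** A wrongly flagged participant with no genuine TEAE in the row adds 1/n, where n is the Safety Population.

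| Assumed n | Shift per participant |
|---|---|
| 8 | 1/8 = 12.5 points |
| 10 | 1/10 = 10.0 points |
| 12 | 1/12 = 8.3 points |

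None of these is a stated Safety Population. The 8 is the evaluable target (SAP 2.5), the 12 is the number of adults with BMD given at least one dose of EDG-5506 by May 8th, 2022 (Protocol 2.3.1), and 10 lies between them. A participant who already has a genuine TEAE in the row adds 0.

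**6. Chance of any affected record.** The documents give no rate. If each of 8 participants independently had probability p of such a record, the chance of at least one is 1 - (1 - p)^8: 7.7% at p = 1%, 33.7% at 5%, 57.0% at 10% and 83.2% at 20%. The p values are assumptions, and the range is too wide to predict a count.

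**The case against.** The best reply is that this is a slip of wording whose intended form already stands in 3.1.7 item 4, and that a sensible programmer would follow the definition. That is probably what was meant. But the last sentence is a specific instruction, and a literal reading produces the wrong flag. The programming specifications are a separate document (SAP section 6) and cannot be assumed to correct it.

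A second reply is that the rule is deliberately conservative. SAP 3.1.7 does state a conservative principle, but for missing components of a date. Here the date is known, so there is no uncertainty to resolve, and every item of the 3.1.7 algorithm keeps an exemption for events that ended before dosing.

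The objections to the size of the effect stand:

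- The affected set is narrow. SAP 3.1.7 expresses AE duration in days, hours and minutes, which suggests that times are meant to be recorded.
- Dosing runs for up to 24 months and dizziness and drowsiness are among the most common AEs. Most participants may have a genuine TEAE anyway, so the any-TEAE row may not move. Any effect would fall mainly on individual organ-class or preferred-term rows.
- In Appendix A, Tables 14.3.2.1 to 14.3.2.3 are titled for adverse events generally. Only 14.3.2.4 names TEAEs, and a brief pre-dose event is unlikely to lead to drug discontinuation.
- There is no comparator. The error can only add events, and all-AE and all-SAE counts do not use the flag, so no safety signal would be hidden.

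**Conclusion.** The point holds as a minor correction. The last sentence of SAP 3.1.8 contradicts the definition and date comparison in the same section for every AE that starts before the first-dose date, lacks an onset time, and neither worsens nor re-emerges. It also contradicts 3.1.7 item 4 for the rare Day 1 event shown to have ended before dosing. AEs that re-emerge or worsen on treatment are genuine TEAEs and are not in question.

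The textual conflict is certain; whether any count changes is not. The number of affected records is unknown, probably small and possibly zero. The shift of 8.3 to 12.5 points per wrongly counted participant rests on an assumed Safety Population of 12 down to 8, and on that participant having no genuine TEAE in the row. This reads the dose date in the sentence as the date of first dose, as the context suggests. Read as the date of any dose, the rule would be looser still.

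**What to change.** Replace the last sentence of SAP 3.1.8 with text along these lines: *If the onset time is missing and the start date is the same as the date of first dose of EDG-5506, the AE is a TEAE unless its recorded end date and time show that it was over before that dose. An AE with a start date before the date of first dose is a TEAE only if it re-emerges or worsens during treatment.* The second sentence restates the existing definition, but it removes any doubt about which rule governs pre-dose events.

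The cost is one sentence reworded, one added, and one derivation line in the AE dataset, with no new data and no patient burden. It belongs in the SAP before database lock. After lock, SAP section 1 requires the change to be documented in the CSR.

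A separate small clean-up could be made in the same edit. SAP 3.1.7 says both that missing date components take the most conservative value and that no dates are imputed, while 3.5.1.2 says dates will be imputed to determine treatment emergence. Short edits in those two sections would reconcile them.
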